10.2. Definition of a Serious Adverse Event (SAE)

An SAE is a particular category of AE where the adverse outcome is serious. If an event is not an AE per definition above, then it cannot be an SAE even if serious conditions are met.

A serious adverse event is any untoward medical occurrence at any dose that:

- **Results in death**
- **Is life-threatening**
 - The term 'life-threatening' in the definition of 'serious' refers to an event in which the participant was at risk of death at the time of the event. It does not refer to an event, which hypothetically might have caused death, if it were more severe.
- **Requires inpatient hospitalization or prolongation of existing hospitalization**
 - In general, hospitalization signifies that the participant has been detained (usually involving at least an overnight stay) at the hospital or emergency ward for observation and/or treatment that would not have been appropriate in the physician's office or outpatient setting. Complications that occur during hospitalization are AEs. If a complication prolongs hospitalization or fulfills any other serious criteria, the event is serious. When in doubt as to whether hospitalization occurred, or was necessary, the AE should be considered serious.
 - Hospitalization for elective treatment of a pre-existing condition that did not worsen from baseline is not considered an AE.
- **Results in persistent or significant disability /incapacity**
 - The term disability means a substantial disruption of a person's ability to conduct normal life functions.

- This definition is not intended to include experiences of relatively minor medical significance such as an uncomplicated headache, nausea, vomiting, diarrhea, influenza, and accidental trauma (e.g., sprained ankle) which may interfere with or prevent everyday life functions but do not constitute a substantial disruption.

- **Results in congenital anomaly/birth defect**

- **Other situations:**

- Medical or scientific judgment should be exercised in deciding whether SAE reporting is appropriate in other situations, such as important medical events that may not be immediately life-threatening or result in death or hospitalization, but may jeopardize the participant or may require medical or surgical intervention to prevent one of the other outcomes listed in the above definition. These events should usually be considered serious.
- Examples of such events include invasive or malignant cancers, intensive treatment in an emergency room or at home for allergic bronchospasm, blood dyscrasias or convulsions that do not result in hospitalization, or development of drug dependency or drug abuse.

Note: Classification of an AE as 'serious' is based on the outcome of the event and is a factor in determining reporting requirements.

10.3 Expected Events

UV Expected Events:

Possible/expected side effects on and/or around the test sites associated with UV exposure include the following:

- Erythema (sunburn)
- Mild discomfort
- Itching
- Edema (swelling)
- Dryness/Tightness
- Peeling
- Papules
- Stinging/Burning
- Ulceration or irritation
- Heat
- Hyperpigmentation/hypopigmentation are possible

Any expected side effects experienced by the participant after UV exposure of the test sites are not to be considered AEs. Test products may not perform up to the expected protection level. Under protection outcomes are potential anticipated events and are also not to be considered AEs. However, if any of these parameters/outcomes appear

to be highly exacerbated, more than normally associated with the test procedures as determined by the PI, or designee, and lead to discontinuation, the event will be documented as an AE.

Skincare Product Expected Events:

There is always the possibility of irritation or a skin reaction to any product applied to the skin. Examples of possible skincare product reactions are:

- Redness
- Dryness/tightness
- Peeling
- Itching
- Burning/stinging
- Allergic reaction

Any skin reaction associated with the application of a test product to the test site will be considered an AE and documented as such.

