5.4 Participant Discontinuation and Withdrawal

A participant may be discontinued or withdraw from study participation at any time if the participant or the PI (or designee) feels it is not in their best interest to continue. The following is a list of possible reasons for study discontinuation.

- Participant develops a condition listed in the exclusion criteria or hypersensitivity, or takes a contra-indicated medication/treatment.
- Non-compliance with the requirements of the protocol.
- Failure to follow site staff instructions.

- Failure to attend scheduled study visits.
- Adverse event (AE) that, in the opinion of the PI, means it would be in the best interest to discontinue study participation.
- Protocol violation requiring documentation of deviation.
- Sponsor request for early termination of study.

Participants are free to withdraw from study participation at any time, for any reason, specified or unspecified, and without prejudice. Reasonable attempts will be made by the PI, or designee, to ascertain the reason for withdrawal. This will be recorded in source documentation and included in the final report.

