10.0 Adverse Events

The safety population is defined as all randomized participants who received at least one dose of a study treatment.

The PI, or designated designee(s), is responsible for detecting, documenting and reporting events that meet the definition of an AE or SAE.

The PI, or designated designee(s), is responsible for following up serious AEs (SAEs); AEs considered to be test product (or study procedure) related; and AEs that caused the participant to discontinue or be withdrawn from the study.

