10.1 Definition of an Adverse Event (AE)

An AE is any untoward medical occurrence in a clinical study participant, temporally associated with the use of a test product, whether or not considered related to the test product. An AE can therefore be any unfavorable and unintended sign (including an abnormal laboratory finding), symptom, or disease (new or exacerbated) temporally associated with the use of a test product.

Events Meeting the AE Definition:

- Unexpected or unusual reactions which occur within a test site that cannot be completely described by the scale in Table 8 (e.g., hives) will be recorded as AEs.
- Any abnormal laboratory test results (hematology, clinical chemistry, or urinalysis) or other safety assessments (e.g., ECG, radiological scans, vital sign measurements), including those that worsen after test product administration, considered clinically significant in the medical and scientific judgment of the PI or medically qualified designee (i.e., not related to progression of underlying disease).
- Exacerbation of a chronic or intermittent pre-existing condition including either an increase in frequency and/or intensity of the condition after test product administration.
- New conditions detected or diagnosed after test product administration, even though it may have been present before the start of the study.
- Signs, symptoms, or the clinical sequelae of a suspected drug-drug interaction.
- Signs, symptoms, or the clinical sequelae of a suspected overdose of either test product or a concomitant medication. Overdose per se will not be reported as an AE/SAE unless it is an intentional overdose taken with possible suicidal/self-harming intent. Such overdoses should be reported regardless of sequelae.
- Lack of efficacy per se will not be reported as an AE. Such instances will be captured in the efficacy assessments. However, the signs, symptoms, and/or clinical sequelae resulting from lack of efficacy will be reported as AE if they fulfill the definition of an AE.

Events NOT meeting the AE definition:

- Any clinically significant abnormal laboratory findings (if applicable) or other abnormal safety assessments which are associated with an underlying disease, unless judged by the PI, or medically qualified designee, to be more severe than expected for the participant's condition.

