- A medical or surgical procedure (e.g., endoscopy, appendectomy) is not an AE. The condition that leads to the procedure is the AE (e.g., gastritis, appendicitis).
- Situations where an untoward medical occurrence did not occur (social and/or convenience admission to a hospital).
- Anticipated day-to-day fluctuations in a pre-existing disease/condition present or detected at the start of the study that did not worsen.
- Localized erythema caused by exposure of the skin to UV radiation is expected and will not be reported as an adverse event.

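### Section 10.3 makes a highly exacerbated UV or under-protection reaction an AE only if it leads to discontinuation; this does not fit Section 10.1, and no precedence is stated

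*Combined protocol and SAP*

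**What the plan says.** **Protocol 10.3 (Expected Events).** The section lists effects expected after UV exposure, including erythema, edema, papules and ulceration, and says they are not AEs. It treats poor product performance the same way: "Under protection outcomes are potential anticipated events and are also not to be considered AEs". The exception has two parts joined by a conjunction. The reaction must be highly exacerbated in the judgment of the PI or designee "and lead to discontinuation, the event will be documented as an AE". A separate paragraph covers reactions to the product itself, with no such condition: "Any skin reaction associated with the application of a test product to the test site will be considered an AE and documented as such".

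**Protocol 10.1 (Definition of an AE).** Three entries bear on the same reactions:

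- Recorded as AEs: "Unexpected or unusual reactions which occur within a test site that cannot be completely described by the scale in Table 8".
- Lack of efficacy is not itself an AE, but its signs, symptoms and "clinical sequelae resulting from lack of efficacy will be reported as AE if they fulfill the definition of an AE".
- Among the events that do not qualify: "Localized erythema caused by exposure of the skin to UV radiation is expected and will not be reported as an adverse event".

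None of the three mentions discontinuation, and neither section says which one governs.

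**The concern.** Whether a reaction is an AE should depend on the reaction. Under 10.3 it depends also on whether the participant stopped. Two people with the same abnormal skin reaction could be recorded differently because one left the study and the other completed it. Two staff members could also record the same reaction differently, one following 10.1 and the other 10.3.

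What is at stake is the safety record. Section 15.0 requires each of the three study reports to summarise AEs and SAEs or to state that none occurred. That statement should not turn on which section the site followed.

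**Working it through.** There is no sample-size or error-rate figure to reproduce. The check sets the two sections side by side, reaction by reaction, and then looks at timing.

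1. **Localized UV erythema, highly exacerbated, participant discontinues.** 10.1: not reported, no exception. 10.3: erythema is on the list and both conditions are met, so it is an AE. This is a direct contradiction.

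2. **A listed effect outside the grading scale, judged beyond the usual test response, participant completes.** Table 8 grades only erythema, borders and edema, so ulceration or papules cannot be fully described by it. 10.1: an AE, if a reaction beyond the normal response counts as unusual. 10.3: not an AE, because nobody discontinued. The two overlap with opposite answers, subject to that reading of unusual.

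3. **Signs or sequelae of under-protection, participant completes.** 10.1: an AE if the general definition is met. 10.3: not an AE. It is unclear whether 10.3 settles the question that 10.1 leaves to the definition, so this is an ambiguous overlap.

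4. **Timing.** By Table 4, the repeat unprotected site, the SPF standard and the test-product sites are irradiated on Day 2. They are evaluated 16 to 24 hours later on Day 3, which is also marked as study conclusion. After that evaluation no scheduled procedure remains to discontinue. AE collection nevertheless continues under 10.4 until 14 days after the last product application or procedure, although 10.4 does not oblige the PI to seek events actively once participation has ended. For a reaction first seen at or after Day 3, the second condition can therefore seldom be met. It can operate earlier: Immediate Response Codes are recorded after irradiation, and 5.4 allows discontinuation at any time.

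5. **Seriousness.** 10.2 says that an event outside the AE definition above it cannot be an SAE. That wording points to 10.1, yet 10.3 also says what is not an AE. Whether a reaction excluded only by 10.3 is to be assessed for seriousness is unclear.

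6. **Would deleting the condition be enough?** No. It removes the dependence on discontinuation in cases 2 and 3. In case 1 it would widen the contradiction, since 10.3 would then admit exacerbated erythema whether or not the participant stopped, while 10.1 still excluded it. Case 3 would also stay open for reactions short of highly exacerbated. The sections have to be reconciled as well.

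**The case against.** The strongest reply is that the sections complement each other: 10.1 deals with unexpected reactions, with hives as its example, and 10.3 with expected ones. On lack of efficacy, 10.1 applies only when the AE definition is met, and 10.3 may be read as settling that for under-protection. This has force, and it is why cases 2 and 3 are called overlaps and not flat contradictions. It does not remove them, because 10.1 covers unusual as well as unexpected reactions and no text assigns precedence. It does not touch case 1.

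It also stands that reactions associated with applying a test product are AEs unconditionally, which narrows the gap at treated sites. It does not reach reactions attributed to UV, or the untreated site. Evaluator comments, optional photographs and source records would still capture what was seen, so the loss is mainly the AE classification and what follows from it.

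Three stronger readings are tempting, and the documents do not support them:

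- *The plan reverses its own logic.* A reader might set 10.3 against 5.4, which lists as a reason to stop an "Adverse event (AE) that, in the opinion of the PI, means it would be in the best interest to discontinue study participation". But 5.4 lists possible reasons and also allows stopping without an AE. Likewise 10.0 names for follow-up "AEs considered to be test product (or study procedure) related; and AEs that caused the participant to discontinue or be withdrawn from the study"; separate groups are consistent with 10.3, since other AEs can occur without discontinuation.
- *Most test sites are affected.* Counting the sites first graded on Day 3 measures when erythema is first graded. It does not show when itching, papules or other disputed reactions are first noticed.
- *Such a reaction can never be an SAE.* The 10.2 wording leaves this ambiguous and does not establish a bar.

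**Conclusion.** The point holds as a **minor** defect in the AE rules. There is one direct contradiction (localized erythema), one overlap that rests on treating a more-than-normal reaction as unusual, and one ambiguous overlap (sequelae of lack of efficacy). Followed as written, 10.3 can leave a highly exacerbated reaction in a participant who completes the study unrecorded as an AE, most plainly when it is first seen at or after Day 3.

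The effect is confined to AE recording, assessment for seriousness and the safety statement in the study reports. SPF values, data-validity rules and the statistical analysis do not change. The documents give no rate for such reactions, so no number of missed events can be stated and none is claimed.

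**What to change.** 1. In 10.3, delete the discontinuation condition from the exception. A UV or under-protection reaction that the PI judges highly exacerbated beyond the normal test response would then be an AE whenever it is seen in the 10.4 collection period, whether or not the participant stopped.
2. Reconcile 10.1 and 10.3 into one UV exclusion with one exception. Place it in 10.1, state that it also covers localized erythema and how it applies to sequelae of lack of efficacy, and have 10.3 refer to it.
3. Cross-reference the exception in 10.2, so that such an event is assessed for seriousness.

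Leave the rule on product-associated skin reactions unchanged. These edits concern event recording only and do not alter when a participant is discontinued. Ordinary graded erythema, on which the SPF endpoint rests, stays excluded. The cost is amendment wording in 10.1 to 10.3 and possibly a few more AE records.

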10.4. Time Period and Frequency for Collecting AE and SAE Information

All AEs, and therefore all SAEs, will be collected immediately after a participant provides consent to participate in the trial by the completion (signing) of the ICF and until 14 days following last administration of test product (or last study procedure). Medical occurrences that began before obtaining informed consent will be recorded in the source documentation as Medical History/Current Medical Conditions, not as AEs.

All SAEs will be recorded and reported to the Sponsor, or designee, immediately and under no circumstance should this exceed 24 hours. The PI, or designee, will submit any updated SAE data to the Sponsor within 24 hours of it being available.

The PI is not obligated to actively seek AEs or SAEs after the conclusion of study participation. However, if the PI learns of any SAE, including a death, at any time after a participant has been discharged from the study, and they consider the event to be reasonably related to the test product or study participation, the PI must promptly notify the Sponsor.

10.5. Reporting Procedures

The PI, or medically qualified designee, is responsible for detecting, documenting and reporting all events that meet the definition of an AE and remains responsible for following up on AEs that are serious or considered to be related to a test product, participation in the study or a study procedure, or that caused the participant to discontinue a test product or the study.

Each participant will be questioned about AEs. Spontaneously reported AEs and those elicited by asking non-directive questions (such as "How do you feel?") will be assessed, recorded in AE-specific source documentation and reported appropriately.

The PI, or medically qualified designee, is to report all directly observed AEs and all AEs spontaneously reported by a participant.

Each AE should be assessed to determine if it meets the criteria for a SAE. If an SAE occurs, expedited reporting will follow local and international regulations, as appropriate.

When an AE occurs, it is the responsibility of the PI, or medically qualified designee, to review all documentation (e.g., hospital progress notes, laboratory and diagnostics reports) related to the event. The PI, or designee, will record all relevant information regarding an AE in AE-specific source documentation and all details relating to an SAE on the paper SAE form provided.

It is not acceptable for the PI, or medically qualified designee, to send photocopies of a participant's medical records to GSK CH in lieu of completion of AE-specific source documentation or the SAE form. There may be instances when copies of medical records are requested by GSK CH. In this instance, all participant identifiers, except for the participant number, will be redacted prior to sharing with GSK CH.

The PI, or medically qualified designee, will attempt to establish a diagnosis of the event based on signs, symptoms, and/or other clinical information. The diagnosis should be documented as the AE/SAE, where known, and not the individual signs/symptoms (e.g., upper respiratory tract infection, seasonal allergy; not cough, runny nose).

AEs elicited by the PI, or medically qualified designee, during study visits should be recorded in AE-specific source documentation and/or using the SAE form, as appropriate. Care will be taken not to introduce bias when questioning a participant about changes in their health. Open-ended and non-directive verbal questioning should be used.

Reporting an Adverse Event:

AEs will be reported using AE-specific source documentation by the PI or site staff and the Sponsor-supplied SAE form, when appropriate, using concise medical terminology. Where the same data are collected, AE-specific source documentation and the SAE form must be completed in a consistent manner; the same AE terms should be used on both.

Reporting a Serious Adverse Event:

In addition to recording the details in AE-specific source documentation, an SAE form should be completed, as fully as possible. Hard copies of the paper SAE form will be provided for the Investigator Site Master File. Original SAE forms should be retained in the Investigator Trial Master File.

It is essential to enter the following information:

- Protocol and participant identifiers

- Participant demography
- Description of event(s), with diagnosis if available
- PI opinion of relationship to test product (or study procedure, if appropriate)
- Criterion for seriousness

The following are desirable and are of particular relevance for PI and GSK CH assessment of the SAE report:

- Date of onset of event
- Date event stopped, if relevant
- Test product start date
- Test product end date, if relevant
- Action taken in relation to the test product
- Outcome if known

The SAE form, completed as fully as possible, must be scanned and e-mailed to the GSK CH Clinical Operations Safety Reporting email box with the GSK CH study number and participant number in the title field of the email **immediately and under no circumstance should this exceed 24 hours** after study site personnel learn of the event. The PI will submit any updated SAE data to the sponsor **immediately and under no circumstance should this exceed 24 hours** of it being available. The GSK CH Study Manager should also be notified of the situation by telephone or email.

Email Serious Adverse Events to:

PPD

The GSK CH Study Manager, or designee, will be responsible for forwarding the SAE form to the Case Management Group, Global Clinical Safety and Pharmacovigilance mailbox PPD [REDACTED]. The initial report will be followed up with more information as relevant, or as requested by the Sponsor.

10.6. Evaluating Adverse Events

Assessment of Intensity:

The PI, or medically qualified designee, will assess intensity for each AE reported during the study and will assign one of the following categories.

- **Mild:** An event that is easily tolerated by the participant, causing minimal discomfort and not interfering with everyday activities.
- **Moderate:** An event that is sufficiently discomforting to interfere with normal everyday activities
- **Severe:** An event that prevents normal everyday activities.

NOTE: An AE classified as **Severe** should not be confused with an SAE.

Severe is a category utilized to classify the intensity of an event; both non-serious AEs and SAEs can be classified as Severe. For example, a headache may be Severe (interferes significantly with the participant's usual function) but would not be classified as Serious unless it met one of the criteria for an SAE, as described above (Section 1.2.2.). An event is defined as 'serious' when it meets at least 1 of the pre-defined outcomes as described in Section 1.2.2., not when it is classified as Severe.

Assessment of Causality

Causality is one of the criteria used to determine regulatory reporting requirements. For each AE (serious and non-serious), the PI, or medically qualified designee, must provide an assessment of causality in the AE-specific source documentation and, for SAEs, on the SAE form.

The PI, or medically qualified designee, will use clinical judgment to determine causality, having also consulted the Safety Statement provided by the Sponsor for this study. Alternative causes, such as underlying disease(s), concomitant therapy, other risk factors and the temporal relationship of the event to the test product will also be taken into consideration and investigated.

There may be situations where an SAE has occurred, and the PI has minimal information to include in the initial report to GSK CH. The PI is required to make an assessment of causality prior to the initial transmission of the SAE form to GSK CH; they may change their opinion of causality in light of follow-up information and send an SAE follow-up report with the updated causality assessment.

Relationship to Test Material

The relationship or association of the AE to test product will be characterized as Unlikely, Possible or Probable (Table 10).

A Reasonable possibility of relationship conveys there are facts, evidence and/or arguments to suggest a causal relationship, rather than a relationship cannot be ruled out. The facts, evidence and/or arguments which suggest a causal relationship should be provided in the AE report.

For safety analyses, AEs classified as a Possible or Probable association to test product shall be considered test product-related AEs.

Follow-up of an AE, after discontinuation of exposure to test product is required if the AE or its sequelae persist. Follow-up is required until the event or its sequelae resolve or stabilize at a level acceptable to the PI and to the Medical Monitor.

Table 10: Causality Assessment

Causality Term	Assessment Criteria
Probable	Event or laboratory test abnormality, with plausible time relationship to test product exposure
	Unlikely to be attributed to condition (or disease) or other products in use by participant
	Response to withdrawal clinically reasonable
	Re-challenge satisfactory or not required
Possible	Event or laboratory test abnormality, with reasonable time relationship to test product use
	Could also be explained by condition (or disease) or other products in use by participant
	Response to withdrawal unclear or lacking
Unlikely	Event or laboratory test abnormality, with a time to test product use that makes a relationship improbable (but not impossible)
	Condition (or disease) or other products provide plausible explanations

